#### Analytic models.

We used logistic multilevel models to examine the impact of training assignment on training completion and engagement in FBT consultation at 12-month follow-up, and linear multilevel models with restricted maximum likelihood (REML) estimation to examine the impact of training assignment on knowledge acquisition at post-training. All models included a random intercept at the agency level. All models included prior FBT experience, baseline attitudes toward evidence-based practice, perceived organizational importance of ED treatment, and training preference as covariates. Analyses of participation in FBT consultation also covaried baseline intent to engage in consultation, and analyses of post-training FBT knowledge also covaried baseline knowledge.

We first examined main effects of training assignment on outcomes, accounting for covariates. We then conducted interaction models to explore whether associations between training assignment and outcomes depended on baseline preference for live versus online training.

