## **Participants**

Participants ( $N = 85$ ) were mental health providers employed in publicly-funded outpatient agencies who were actively seeing youth clients with Medi-Cal insurance within one of the six participating counties. Participants were required to speak and read English. Given the large number of unlicensed clinicians formally working within county behavioral health systems, eligibility did not require clinicians to be licensed, but it did require that unlicensed clinicians be formally employed as clinical staff and have a supervisor licensed in the state of California who was willing to assume legal responsibility for any cases treated.

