## **Randomization**

Randomization to training condition (online vs. live training) was done at the agency level, stratified by agency enrollment (low = fewer than 5 clinician participants, large = 5 or more clinician participants), in a 2:1 ratio for online to live training using a random sequence generator. Following completion of training, participants who completed training and expressed interest in providing care to youth with EDs were offered one year of group-based FBT consultation. Within training condition, participants were assigned to consultation groups based

on individual preferences for consultation group day/time and group capacity. The resulting consultation groups were then randomized using a random sequence generator to receive either 1) expert consultation or 2) expert (6 months) + peer consultation (6 months).

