### Missing data.

We used multivariate imputation using chained equations (MICE), a form of multiple imputation, to account for missingness. MICE models included all variables in the analytic model for a given outcome (dependent and independent variables), as well as several axillary variables to inform imputed values: post-training MPAS score, importance of ED treatment in provider's own practice, total years of experience, licensure status, treatment caseload, training completion (for models in which this was not an outcome), and county (except for supplemental

analyses of any FBT consultation, for which inclusion of county led to convergence issues, likely due to relatively small cell size). Imputation was conducted with predictive mean matching with a knn value of 5 for continuous variables and logistic regression for dichotomous variables. We used 100 imputations with a burn-in period of 100 iterations.

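### The SAP specifies no few-cluster inference for the agency-randomised training effect; with about 20 or fewer agencies and a non-trivial ICC, a large-sample Wald test would exceed its 5% level

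*Combined protocol and SAP*

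**What the plan says.** The Randomization section states: "Randomization to training condition (online vs. live training) was done at the agency level". Allocation was "in a 2:1 ratio for online to live training using a random sequence generator" and "stratified by agency enrollment (low = fewer than 5 clinician participants, large = 5 or more clinician participants". The Participants section gives 85 clinicians. The number of agencies is not given.

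Under Analytic models, the SAP writes "We used logistic multilevel models to examine the impact of training assignment on training completion and engagement in FBT consultation at 12-month follow-up", and for the other primary outcome it uses "linear multilevel models with restricted maximum likelihood (REML) estimation to examine the impact of training assignment on knowledge acquisition at post-training". On clustering it says: "All models included a random intercept at the agency level". Under Missing data it describes chained-equation imputation: "We used 100 imputations with a burn-in period of 100 iterations".

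The SAP names the software (Stata 16.1), but no command or option that would fix the inference. It states no reference distribution, no degrees-of-freedom method for the models or for pooling, no permutation test, no ICC and no alpha.

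**The concern.** Every clinician in an agency has the same training assignment, so training varies only between agencies. At 2:1 the live arm holds about a third of them: 4 of 12, about 7 of 20, or 10 of 30. The uncertainty in the training coefficient is governed by those counts.

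A random intercept puts the agency variance into the standard error, and REML reduces the downward bias in estimating that variance. Neither supplies a reference distribution that allows for the variance having been estimated from few agencies. Ordinary Wald inference for a random-intercept logistic model is also large-sample.

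The gap is common to both primary outcomes and the secondary outcome. If it was filled with a normal reference and the agencies were few, p-values and intervals would be somewhat too favourable, and a borderline difference between online and live training could be reported when there is none.

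**Working it through.** The documents contain no sample-size calculation or error-rate figure to reproduce, so the check asks how a Wald z test behaves in this design when training has no effect.

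**Inputs from the documents:** 85 clinicians; agency randomisation, 2:1, stratified at 5 clinicians; agency random intercept; four covariates in every model and a fifth in the knowledge and consultation models; 100 imputations.

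**Assumptions:** number of agencies K from 8 to 40; residual ICC from 0 to 0.20; two-sided 5% level; unequal agency sizes; clinician-level covariates.

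**Step 1: closed form.** With K agencies in two arms, the between-agency contrast has about K - 2 degrees of freedom. The interval-width ratio is t(0.975, K-2)/1.96. The approximate level of a z test is 2P(t(K-2) > 1.96). For K = 12: 2.228/1.96 = 1.137, and 2P(t(10) > 1.96) = 7.8%.

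**Step 2: simulation of the knowledge model.** REML random-intercept fit, five covariates, complete data, 4,000 runs per setting (Monte Carlo standard error about 0.35 points at 5%). Entries in the last five columns are type I error, %.

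| K | Width ratio | 2P(t>1.96) | z, ICC 0 | z, ICC 0.05 / 0.10 / 0.20 | t(K-2), ICC 0 | t(K-2), ICC 0.05-0.20 |
|---|---|---|---|---|---|---|
| 8 | 1.248 | 9.8% | 3.9 | 7.4 / 9.4 / 10.4 | 1.0 | 3.0-5.4 |
| 12 | 1.137 | 7.8% | 3.9 | 6.4 / 7.9 / 8.4 | 1.9 | 4.1-6.1 |
| 16 | 1.094 | 7.0% | 4.1 | 5.7 / 6.8 / 7.7 | 2.9 | 4.1-5.7 |
| 20 | 1.072 | 6.6% | 4.4 | 6.0 / 6.9 / 7.2 | 3.2 | 4.4-5.6 |
| 30 | 1.045 | 6.0% | 5.1 | 4.6 / 6.2 / 6.1 | 4.0 | 3.8-5.2 |
| 40 | 1.033 | 5.7% | 5.2 | 5.3 / 5.1 / 6.7 | 4.3 | 4.4-5.7 |

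Two separate REML simulations of the same problem agree for ICC 0.05-0.20. One (8,000 runs per setting) gave z error of 6.5-8.0% at 12 agencies, 5.9-7.4% at 18, 5.7-7.0% at 25 and 5.6-6.3% at 35. The other gave about 7.1-7.7% at 12, 6.3-7.6% at 20 and 5.5-5.9% at 30, brought to 4.7-5.8% by t(K-2). At ICC 0 they gave 4.4-4.7% and 4.0-4.5% with z.

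**Step 3: logistic model.** Four covariates, an assumed 70% event rate, about 1,200 runs per setting (standard error about 0.6 points). Type I error with z at ICC 0 / 0.05 / 0.20:

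- 10 agencies: 3.9 / 7.9 / 11.6%
- 20 agencies: 3.7 / 5.1 / 6.7%
- 30 agencies: 3.7 / 5.8 / 4.7%

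With t(K-2), 10 agencies gave 1.3 / 3.1 / 6.1% and 20 agencies 2.4 / 3.4 / 4.6%.

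**Step 4: pooling.** Without a complete-data limit, Rubin's degrees of freedom are (m - 1)/FMI². With m = 100 and an assumed fraction of missing information (FMI) of 0.3, this is 99/0.09 = 1,100 (critical value 1.962). At 0.5 it is 99/0.25 = 396 (1.966). Both are effectively normal, against 2.228 on 10 degrees of freedom. Pooling therefore does not bring in the agency count unless the analyst supplies it. This step is algebra; imputation was not simulated.

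**The case against.** The strongest reply is that silence is not a method. A reader might infer that the plan refers the training coefficient to a normal distribution, and that its intervals are therefore too narrow and its false positives above 5%. The documents support neither step. No reference distribution is stated, and an analyst using Satterthwaite or Kenward-Roger degrees of freedom would comply equally with the text. The inflation also depends on an agency count and an ICC that are not given. At ICC 0 the z test is at or close to its nominal level, and at 30-40 agencies the excess is small or absent. The relevant ICC is the residual one after covariates, including baseline knowledge in the knowledge model, and may be low. This part of the reply stands, and the size of the problem can only be stated conditionally.

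Three narrower points also stand. REML is not itself a fault. The evidence for the logistic models is less precise: at 20 agencies, inflation is visible only at the higher ICC, and the event rate is assumed. And t(K-2) is not perfectly calibrated, because it is conservative when the ICC is low.

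What does not stand is that this is only a request for more detail. The SAP specifies the imputation down to the number of nearest neighbours and the burn-in, yet leaves open a choice that affects the error rate of its main comparisons. A standard method exists that holds the level close to 5% where z does not.

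**Conclusion.** The concern holds in conditional form. It is certain that training varies only between agencies and that the SAP specifies no few-cluster inference for its effect, either in the models or in pooling.

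If the usual large-sample Wald test was used, then with 12-20 agencies and a residual ICC of 0.05-0.20, type I error for the knowledge model is about 6-8% (up to about 10% at 8 agencies). The corresponding t-based 95% interval is about 7-14% wider. The logistic models for training completion and consultation engagement are similarly exposed, with less certainty about the amount. With 30-40 agencies the effect is small, and with an ICC near 0 there is none.

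These sizes rest on an assumed agency count, ICC, agency-size spread and 5% two-sided level, and on complete data. The point deserves correction because it touches all three main comparisons, but it would change a conclusion only for a borderline result.

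**What to change.** - For the knowledge model, use Kenward-Roger or Satterthwaite degrees of freedom.
- For the two logistic models, refer the training coefficient to t with agencies minus 2 degrees of freedom, less one for each agency-level covariate.
- Enter these values as the complete-data degrees of freedom in small-sample (Barnard-Rubin) pooling of the 100 imputations.
- As a check, report a permutation test that re-allocates whole agencies within the two size strata.
- Report the number of agencies per arm, the ICC and the reference distribution used. If a small-sample method was in fact applied, saying so settles most of the point.

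The analyses are described as already done, so the cost is re-running the inference on existing data; no new data are needed. If z was used, complete-data intervals become roughly 3-14% wider at 12-40 agencies and about 25% wider at 8. Barnard-Rubin pooling can widen them further where information is missing. The main drawback is a conservative test on t(K-2) when the ICC is near zero: type I error of about 3%, or 1-2% with 8-12 agencies, with a matching loss of power.

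### Agencies were randomised within enrolment-size strata, but the stratum is in no analysis model; if size predicts knowledge and allocation was balanced, the knowledge-model SE is somewhat too large (minor precision point)

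*Combined protocol and SAP*

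**What the plan says.** The Randomization section of the protocol says that agencies were allocated to training "stratified by agency enrollment (low = fewer than 5 clinician participants, large = 5 or more clinician participants"). On the sequence itself, the same section says only that agencies were assigned "in a 2:1 ratio for online to live training using a random sequence generator". It does not say whether the sequence was blocked within stratum.

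The Analytic models section of the SAP specifies "linear multilevel models with restricted maximum likelihood (REML) estimation to examine the impact of training assignment on knowledge acquisition at post-training". For the two binary outcomes it says: "We used logistic multilevel models to examine the impact of training assignment on training completion and engagement in FBT consultation at 12-month follow-up". It adds: "All models included a random intercept at the agency level". The common covariates are given as: "All models included prior FBT experience, baseline attitudes toward evidence-based practice, perceived organizational importance of ED treatment, and training preference as covariates". Baseline knowledge is added for the knowledge outcome, and baseline intent to engage in consultation for the consultation outcome. The enrolment stratum is not mentioned. REML is named, but no small-sample reference distribution is.

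The Missing data section says: "MICE models included all variables in the analytic model for a given outcome (dependent and independent variables), as well as several axillary variables". The listed auxiliaries include county, but not the enrolment stratum or agency size. No reason is given for leaving the stratum out.

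**The concern.** A stratified design fixes the balance of the stratification factor between arms. An analysis that ignores the factor does not credit that balance, and reports more uncertainty than the design leaves.

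The agency random intercept might seem to cover this, but it does not. It treats the difference between large and small agencies as random between-agency variance. Training is compared between agencies, so that variance enters the SE of the training effect directly. With 85 clinicians (Participants section) and agencies as the unit of randomisation, precision is limited. What is at stake is a little power for knowledge, one of the two primary outcomes.

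**Working it through.** The documents give no power calculation, number of agencies, ICC or size-outcome association, so there is no stated figure to reproduce. The check is of direction and plausible size.

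**Inputs from the documents:** 85 clinicians; agency-level 2:1 allocation; two enrolment strata; a REML random-intercept model with five covariates (four common plus baseline knowledge).

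**Assumptions:** 15, 24 or 36 agencies, 6 of them large; ICC 0.05-0.10; residual size effect d of 0, 0.3 or 0.5 SD after the covariates; total residual variance 1; complete data.

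**1. Hand approximation, balanced allocation.** With equal agency sizes m, the variance of an agency mean given the stratum is ICC + (1 - ICC)/m. Leaving the stratum out adds p(1 - p)d² to the apparent variance, where p is the share of large agencies. Balance keeps that term out of the true sampling variance of the contrast. So

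SE ratio ≈ √{[ICC + (1 - ICC)/m + p(1 - p)d²] / [ICC + (1 - ICC)/m]}.

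For 24 agencies and ICC 0.05: m = 85/24 = 3.54, p = 6/24 = 0.25, and the denominator is 0.05 + 0.95/3.54 = 0.318.

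- d = 0.3: added term 0.1875 × 0.09 = 0.0169; ratio √(0.3351/0.3182) = 1.026.
- d = 0.5: added term 0.1875 × 0.25 = 0.0469; ratio √(0.3651/0.3182) = 1.071.

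Real agencies differ in size by the definition of the strata, so this shows only direction and order of size.

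**2. How strong these size effects are.** The share of between-agency variance due to size is p(1 - p)d² / [p(1 - p)d² + ICC]. Over the assumed range it is 11-30% at 0.3 SD and 26-55% at 0.5 SD. The second is a strong case.

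**3. Simulation, linear knowledge model** (4,000 trials per scenario, training effect 0.6 SD, t reference in both models):

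| Allocation | Size effect | SE without the stratum | Power change from adding it |
|---|---|---|---|
| Balanced | 0 SD | no penalty | -0.4 to -1.6 points |
| Balanced | 0.3 SD | 3-4% too large | +2.1 to +2.8 points |
| Balanced | 0.5 SD | 7-12% too large | +6.0 to +8.7 points |
| Unblocked | 0 SD | valid | -2.3 to -4.0 points |
| Unblocked | 0.3 SD | valid | -1.5 to +0.5 points |
| Unblocked | 0.5 SD | valid | +2.8 to +5.0 points |

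Here, too large means the ratio of model SE to empirical SD without the stratum, divided by the same ratio with it. With unblocked allocation the ratio of SE to SD was 0.97-1.04. The bias from leaving the stratum out was at most 0.012 SD (balanced) and 0.020 SD (unblocked).

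**4. Second simulation with other layouts** (21 agencies with 79 clinicians, 27 agencies with 85; ICC 0.02 or 0.10; 2,000 trials). With balanced allocation the SE without the stratum, divided by the SE with it, was about 1.00 at 0 SD, 1.03 at 0.3 SD and 1.09-1.10 at 0.5 SD. With unstratified allocation the ratio of SE to SD without the stratum was about 1.00. This agrees with step 3.

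**5. Type I error of the unadjusted test with a z reference.** In the step 4 runs it was 4.3-5.3% at 0.3 SD and 3.3-4.2% at 0.5 SD. In further runs at ICC 0.05 with 15, 24 and 36 agencies it was 5.4, 5.2 and 5.1% at 0.3 SD, and 4.4, 3.6 and 3.6% at 0.5 SD.

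**6. Logistic completion model** (ICC 0.10, 15 or 24 agencies, balanced, t reference, 600 trials). At a stratum log-odds ratio of 0.5 the apparent gain is 3-4 points. About 1.3-1.7 points also appear with no stratum effect, which leaves roughly 1.3-2.7 (3 - 1.7 to 4 - 1.3). The unadjusted ratio of SE to SD was 0.95-1.00, so the SE is not overstated.

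The engagement model, the preference-interaction model and pooling over imputations were not tested.

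**The case against.** **Both conditions are unknown.** Size must predict knowledge beyond five covariates, baseline knowledge among them, and allocation must have been balanced within stratum. The documents establish neither. This stands, and it is why the size is given as a range.

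**A reader might infer that the knowledge test is conservative.** The documents do not support that as a general statement. It depends on a reference distribution that the SAP does not name. With t, the unadjusted test ran at 2.6-3.8% at 0.5 SD. With z it is about nominal at 0.3 SD and at most mildly conservative at 0.5 SD.

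**The power gains hold only with the same reference in both models.** If a small-sample reference is introduced together with the stratum, z without the stratum against t with it gives a net loss of about 0.3-5 points at 0.3 SD, and a gain of only about 1-4 points at 0.5 SD (balanced). This also stands. The small-sample reference is a separate question of type I error: with 15 agencies the adjusted z test ran at 5.7-7.0%, while t gave 3.7-5.3% over 15-36 agencies.

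**A reader might extend the point to every model.** The support is weak. The logistic gain is small, and the adjusted logistic test ran at 5.8-9.0% with z and 4.8-6.8% with t, with about 2 points of simulation error. The Missing data section reports that in supplemental consultation analyses "inclusion of county led to convergence issues, likely due to relatively small cell size", so sparse data are a documented risk. No harm has been shown from the absence of the stratum among the auxiliaries in itself.

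**Conclusion.** The point holds as a minor one about precision. The stratum used to randomise agencies is missing from the models, and the random intercept does not stand in for it. If size is prognostic for knowledge and allocation was balanced, the SE for training is about 3-4% too large at 0.3 SD and 7-12% at 0.5 SD, with 2-3 and 6-9 points of power lost under a common reference distribution. If allocation was unblocked, the SE is valid and adjustment helps only when size is clearly prognostic.

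A reader might go further and infer a biased training effect or an invalid test. The checks show no material bias and no type I inflation from the omission. The figures rest on assumed agency counts, ICC, size effects and blocking, and on complete data. Low priority; a cheap improvement.

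**What to change.** - **Knowledge model:** add the two-level enrolment stratum as a fixed effect. Under the SAP's rule that imputation models contain all analysis-model variables, this also carries it into the imputation for that outcome.
- **Randomization section:** state whether allocation was blocked within stratum. This settles one of the two conditions.
- **Completion and engagement models:** add the stratum only as a sensitivity analysis, after a convergence check. In simulation it added at most 0.2 points to failed logistic fits (worst case 2.5% to 2.7%). It added 0.4-2.5 points to unidentified logistic imputation models with county included, and 0-1.0 point without county.
- **Timing:** the SAP is written in the past tense. If the analysis is final, report the stratum-adjusted knowledge result as a labelled sensitivity analysis beside the analysis as specified, not in its place.
- **Small-sample reference:** decide on t or Kenward-Roger separately, and report its power cost separately.

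The cost is one agency-level degree of freedom. If size is not prognostic, power falls by about 0-1.6 points with balanced allocation, or 2-4 points with unblocked allocation. No new data are needed, because the stratum was recorded for randomisation.

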## **Study Protocol**

The Optimizing Provider Training in Eating Disorders (OPTED) trial is a cluster randomized hybrid type III effectiveness-implementation trial that compared two different training methods and two different types of post-training implementation support for behavioral health providers working in publicly-funded settings over a 12-month period ([NCT 05389657](#)). Given the nested design, randomization to training (online asynchronous self-paced online training vs. live virtual training) was done at the agency level. Following completion of training, interested participants were randomized to consultation groups (expert only vs. expert + peer consultation). Study procedures were approved by the Institutional Review Board at the University of California, San Francisco.

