### **FBT Training**

Although the primary focus of the training was in FBT for restrictive eating disorders, training also incorporated foundational knowledge in ED assessment and overarching ED treatment principles. Substantial education was provided about the psychological and medical consequences of EDs and appropriate medical management, given the importance placed in FBT on emphasizing the severity of the ED and urgency of treatment. The training emphasized that the implementation of FBT is flexible. Families determine the best way to support their child, and clinicians adapt treatment to the family's characteristics, strengths, constraints, culture, and values, while still following the key tenets of FBT. Adaptations to the training were made in response to learning from prior dissemination and implementation efforts, considering the needs of clinicians who work with lower-resourced families and/or work in lower-resourced settings. Clinical considerations and resources specific to lower-income, racially and ethnically diverse populations who are served in publicly-funded settings were added (e.g., flexibility with different family members' roles and methods of engaging in treatment, additional focus on addressing mental health stigma and externalizing the illness), while still emphasizing how to retain fidelity to core treatment principles. A resource library was also created that was accessible to all participants via a shared Box folder, including resources for clinicians and patients/caregivers in both English and Spanish given the high number of Spanish-speaking youth with EDs insured by Medi-Cal and their families. The content presented was identical in both trainings to minimize differences in *what* was presented and for *how long* (14 hours of active content), but the *who*,

*how, and when* differed.

Online training. Participants in the online training condition were allowed to progress through a module-based course on the web-based platform as desired, with a goal of completion within eight weeks. The online self-guided version was on a web-based platform hosted by the 3C Institute, which the study team designed in collaboration with software developers. Training videos were primarily delivered by an expert FBT clinician. Additional training videos were delivered by one of the treatment developers, a pediatrician/child psychiatrist, and a dietitian with extensive expertise in EDs.

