### Primary outcomes.

*Training completion.* Clinician completion of training (yes/no) measured 10 weeks from the start of WBT, and on day 2 of the live training, was used as an initial metric of training reach, adoption, and acceptability. To be considered as having completed training, participants were required to complete 100% of their assigned training (i.e., completing every lesson of the online training, or attending the full two days of training).

*Knowledge acquisition.* The FBT Knowledge Assessment (FBT-KA) is an 18-item measure co-created by the first author that assesses knowledge about FBT for AN and atypical AN, which was administered at pre-training, post-training, and follow-up (6 and 12 months). The assessment focuses on general knowledge about FBT (e.g., contraindications, treatment phases),

key principles (e.g., externalization, agnosticism, clinician as consultant), and key procedures (e.g., taking regular open weights).

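### Do two unranked primary outcomes, with no stated significance level or multiplicity rule, call for a change to the analysis plan?

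*Combined protocol and SAP*

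**What the plan says.** The Primary outcomes section of the protocol holds two entries. Training completion is a yes/no measure that "was used as an initial metric of training reach, adoption, and acceptability". It is met by "completing every lesson of the online training, or attending the full two days of training". Knowledge acquisition is the score on the 18-item FBT Knowledge Assessment, collected before training, after training, and at 6 and 12 months. Neither outcome is placed above the other.

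The Analytic models section of the SAP treats them one at a time. For the first: "We used logistic multilevel models to examine the impact of training assignment on training completion". For the second, a linear multilevel model fitted by REML is used "to examine the impact of training assignment on knowledge acquisition at post-training". The only ordering is between kinds of model: "We first examined main effects of training assignment on outcomes, accounting for covariates". Exploratory interactions with training preference come after that.

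The opening paragraph of the Study Protocol describes a trial that "compared two different training methods and two different types of post-training implementation support". It names no outcome as the deciding one. The text supplied for review states no significance level, sidedness, success criterion, hierarchy or multiplicity adjustment. It also does not say that the absence of adjustment is deliberate.

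**The concern.** Two primary outcomes without a rule for combining them is a familiar weakness. If one were significant and the other not, the document would not say what the trial had concluded about training format, and with no stated level a reader could not say what significant means.

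The two outcomes could well disagree. Completion reflects reach and acceptability. Knowledge compares what clinicians took from material of which the protocol says "The content presented was identical in both trainings to minimize differences in" what was presented and for how long. A difference on one does not imply a difference on the other. If authors could headline whichever outcome succeeded as showing the better format, the false-positive rate for that headline would exceed the level of either test.

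**Working it through.** The plan gives no figure to reproduce: it states no alpha, power or sample-size calculation. The question is which reading the text supports, and what each reading would imply.

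**Inputs.** Two primary outcomes (Primary outcomes section) and one main-effect test for each (Analytic models section). Engagement in consultation is labelled secondary and the interaction models are exploratory, so neither enters the primary count. Knowledge is measured at four times, but the SAP models it as a primary outcome only at post-training, so the count stays at two. Assumed, because the documents are silent: two-sided alpha of 0.05, and each test holding its nominal level. The second assumption is not guaranteed in a cluster-randomised trial of 85 clinicians whose number of agencies is not given.

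**Reading 1: each outcome carries its own conclusion.** The error rate for the completion claim is 0.05 and for the knowledge claim 0.05. No claim draws on both tests, so no adjustment is needed.

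**Reading 2: either result alone shows the better format.** With independent tests and no effect on either outcome:

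- P(at least one rejects) = 1 − (1 − 0.05)² = 0.0975.
- With correlated tests (bivariate normal) this falls to 0.0907 at correlation 0.5, 0.0704 at 0.9 and 0.0566 at 0.99.
- Over an assumed alpha from 0.01 to 0.10, the independent value runs from 1 − 0.99² = 0.0199 to 1 − 0.90² = 0.19.

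**Reading 3: both must succeed, in favour of the same format.** Independent tests, two-sided 0.05:

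- Neither outcome affected: 2 × 0.025 × 0.025 = 0.00125, or 0.125%. Counting rejections in any direction gives 0.05² = 0.0025, but opposite directions would not support a single better format.
- One outcome unaffected, the other with 80% power: about 0.80 × 0.025 = 0.02, against 0.80 × 0.05 = 0.04 if direction is ignored.
- Both are below 0.05, so this reading needs no adjustment either.

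Only Reading 2 inflates error.

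**Which reading does the text support?** The SAP names training completion and post-training knowledge each as the target of its own model, and it refers to effects on outcomes in the plural. Nothing pools them, and no sentence speaks of an overall better format. The protocol confines completion to an initial metric of reach, adoption and acceptability. The opening sentence about two training methods describes the design, and it covers two kinds of post-training support as well. The wording fits Reading 1.

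**What would a Holm step cost?** Holm tests the smaller p-value at 0.025. An outcome with 80% power at 0.05 has a standardised effect of 1.960 + 0.842 = 2.802. At 0.025 the critical value is 2.241, so power is Φ(2.802 − 2.241) = Φ(0.561) = 0.712. When the other outcome is unaffected and independent, the second step adds 0.025 × (0.800 − 0.712) = 0.002, giving about 0.715. That is roughly 8.5 percentage points lost to protect against a claim the plan does not make.

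**The case for a change.** The strongest counter-argument is that silence is itself the fault. The separate-conclusions reading is reasonable, but the plan does not state it. With two unranked primaries and no level, authors keep the freedom to frame the result once they have seen it. The main-effects-first sentence does not help, because it orders model types and not the two outcomes. Two or three sentences would close the gap at no cost in power.

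Much of this stands. The level and the interpretation rule are absent, and stating them would be better practice. It does not carry the point further, for three reasons. First, the added sentences would record a policy and leave every model, estimate and p-value as it is. Second, the document is written in the past tense, with the analyses already done, so a rule inserted now would be post hoc and could not remove the freedom complained of. Third, the harm needs a combined claim about format that appears nowhere in the text.

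Two neighbouring matters do not add weight. The later knowledge assessments are settled for analysis by the SAP's choice of post-training. That completion requires different acts in the two arms is a question of outcome definition, not of multiplicity.

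**Conclusion.** The observation is accurate but calls for no change. Two outcomes are listed as primary, they are modelled separately, and the text supplied gives no significance level, success rule or multiplicity rule. No error inflation follows from the plan as written. The 9.75% figure depends on an assumed two-sided 0.05, independent tests at their nominal level, and an either-outcome claim that the document does not make. Under the reading its wording supports, each primary stands alone at its own level and the adjustment due is nil.

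What remains is a gap that careful analysts fill in the ordinary course of reporting: naming the level used, presenting completion and post-training knowledge as two separate results with confidence intervals, and being open that this reading was not written into the plan. The conclusion would change only if a report used one significant primary as proof that one format is better overall. It also rests on the text supplied, since some front matter was removed and the registry record was not available.
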